6.7.7.1 Adverse events

6.7.7.1.1 Definitions

An Adverse Event (AE) is any adverse change i.e. any unfavorable and unintended sign, including an abnormal laboratory finding, symptom or disease that occurs in a subject during the course of the study, whether or not considered by the investigator as related to the use of IMP.

AEs include:

- Exacerbation of a pre-existing disease.
- Increase in frequency or intensity of a pre-existing episodic disease or medical condition.
- Disease or medical condition detected or diagnosed during the course of the study even though it may have been present prior to the start of the study.
- Continuous persistent disease or symptoms present at study start that worsen following the start of the study.
- Abnormal assessments, e.g., change on physical examination, ECG findings, if they represent a clinically significant finding that was not present at study start or worsened during the course of the study.

Abnormal laboratory values or test results should be reported as adverse events only if they fulfill at least one of the following criteria:

- they induce clinical signs or symptoms,

- they are considered clinically significant,
- they require therapy or
- they result in dose reduction, interruption or permanent discontinuation of IMP administration.

Overdose, misuse, and abuse of the IMP should be reported as an AE and, in addition, IMP errors must be documented in the IMP log of the eCRF.

6.7.7.1.2 Intensity of adverse events

The intensity of clinical AEs is graded on a three-point scale (mild, moderate and severe) as follows:

- Mild

The event may be noticeable to the subject. It does not influence daily activities, and usually does not require intervention

- Moderate

The event may make the subject uncomfortable. Performance of daily activities may be influenced, and intervention may be needed.

- Severe

The event may cause noticeable discomfort, and usually interferes with daily activities. The subject may not be able to continue in the study, and treatment or intervention is usually needed.

If the intensity of an AE worsens during the study, only the worst intensity should be reported on the AE page. If the AE lessens in intensity, no change in the severity is required.

If an AE occurs during the screening period (i.e. after signature of informed consent up to IMP initiation) and worsens after IMP initiation or during the follow-up period, a new AE form must be entered with the appropriated intensity.

A mild, moderate, or severe AE may or may not be serious (see Section 6.7.7.2.1 for definition of SAE). Medical judgment should be used on a case-by-case basis.

6.7.7.1.3 Relationship to investigational medicinal product

Each AE must be assessed by the investigator as to whether or not there is a reasonable possibility of causal relationship to the IMP administration and reported as either related or unrelated. The determination of the likelihood that the IMP caused the AE will be provided by an investigator who is a qualified physician

6.7.7.1.4 Adverse event reporting

All AEs occurring after IMP initiation and up to end-of study (EOS) must be recorded on specific AE forms of the eCRF.

6.7.7.1.5 Follow-up of adverse events

All AEs should be followed until they are resolved, or the investigator assesses them as stable, or the subject's participation in the study ends, i.e., last scheduled visit (Study Completion).

All AEs assessed by the investigator as related to the IMP should continue to be followed until they resolve or until the investigator assesses them as "stable", including after EOS. In the latter case, no changes to eCRF are made.

6.7.7.2 Serious Adverse Events

6.7.7.2.1 Definitions of SAE

An AE that meets one or more of the following criteria/outcomes is classified as serious if:

- Results in death.
- Is life-threatening (i.e., at immediate risk of death).
- Requires in-patient hospitalization or prolongation of existing hospitalization.
- Results in persistent or significant disability/incapacity.
- Is a congenital anomaly/birth defect (i.e., in an offspring to the study subject).
- Is a medically important AE.

Medically important AEs are events that may not result in death, be life threatening, or require hospitalization but may be considered serious when, based upon appropriate medical judgment, may jeopardize the patient or subject or may require medical or surgical intervention to prevent one of the outcomes listed above. Examples of such events are intensive treatment in an emergency room or at home for allergic bronchospasm, blood dyscrasias or convulsions that do not result in hospitalization or development of dependency or abuse.

The following reasons for hospitalization are exempt from being reported:

- Hospitalization for social and/or convenience reasons.
- Hospitalization for pre-planned (i.e., planned prior to signing informed consent) surgery or standard monitoring of a pre-existing disease or medical condition that did not worsen.

However, complications that occur during hospitalization are AEs or SAEs (for example if a complication prolongs hospitalization or is medically significant as defined above).

6.7.7.2.2 Reporting of SAEs

During screening, administration of IMP and follow-up period

All SAEs occurring after study start (i.e., signing of informed consent) up to EOS must be reported on the SAE form and recorded in the AE pages of the eCRF.

After EOS

New SAEs occurring after the EOS must be reported to the Sobi safety department within 24 hours of the investigator's knowledge of the event, only if considered by the investigator as causally related to previous exposure to the IMP.

6.7.7.2.3 Follow-up of SAEs

SAEs still ongoing at the EOS must be followed up until resolution or stabilization.

6.7.7.2.4 Reporting procedures

All SAEs must be reported by the investigator to Sobi safety department within 24 hours of the investigator's first knowledge of the event.

All SAEs must be recorded on an SAE form, irrespective of the study treatment received by the subject, and whether or not this event is considered by the investigator to be related to IMP.

SAE forms must be emailed to Sobi safety department and Sobi Study Physician (contact details are provided on the SAE form). The investigator must complete the SAE form in English, must assess the causal relationship of the event to IMP and sign the report.

Follow-up information about a previously-reported SAE must also be reported within 24 hours of receiving it. The Sobi safety department may contact the investigator to obtain further information.

If the subject is hospitalized in a hospital other than the study site, it is the investigator's responsibility to contact this hospital to obtain all SAE-relevant information and documentation.

The reference safety document to assess expectedness of a suspect serious adverse reaction and for reporting by the sponsor to Health Authorities, ECs/IRBs and investigators is the reference safety information section of the current version of the Investigator Brochure (IB).

6.7.7.2.5 Pregnancy

There are no data from the use of emapalumab in pregnant women. Animal studies do not indicate direct or indirect harmful effects with respect to reproductive toxicity (see IB).

Females of childbearing potential should not get pregnant during the study and should agree to use appropriate contraception (see Section 6.5.1).

6.7.7.2.6 Reporting of pregnancy

Any pregnancy occurring after IMP administration up to the EOS must be reported within 24 hours of the investigator's knowledge of the event.

Pregnancies must be reported on the Sobi pregnancy form and e-mailed to the Sobi safety department.

6.7.7.2.7 Follow-up of pregnancy

Any pregnancy must be followed to its conclusion, and its outcome must be reported to the Sobi safety department.

Such follow-up information will only be entered in the sponsor's safety database, and hence will not affect study closure. Table 5 presents the laboratory assessments.

Table 5 **Laboratory Assessments**

Biochemistry	Hematology
Aspartate aminotransferase (AST)	Hemoglobin
Alanine aminotransferase (ALT)	Hematocrit
Direct Bilirubin	Platelet count
Total Bilirubin	White blood cells
Uric acid	Red blood cells
Alkaline phosphatase	Differential blood count
Total Protein	Immunoglobulin levels
Albumin	Coagulation profile (APTT)
Prothrombin Time/International Normalized Ratio (PT-INR)	
Fibrinogen	
Complement C3/C4	
Cardiac troponin	
Creatinine	
C-reactive protein (CRP)	
Electrolytes (Sodium, Potassium, Calcium)	
Glucose	
Lipids (fasting (except screening) triglycerides, HDL, LDL)	
BUN/Urea	
Urinalysis (dipstick)	
	Erythrocytes, Leukocytes
	Glucose
	Ketones
	pH
	Protein
	Sediment (only if positive results are obtained for Protein, Erythrocytes and leukocytes measurements)
	Urine pregnancy test
Additional testing at screening	
	TB screening (Quantiferon/T-spot)
	PCR SARS-CoV-2
	Viral serology and infections (HBV, HCV, HIV and syphilis)
	Microbiology testing (stool) for shigella and salmonella bacteria
	s-HCG
	Drug screen;
	Benzodiazepines, cocaine, methamphetamines, marijuana, barbiturates, morphine, Phencyclidines and tricyclic antidepressants

All laboratory samples will be analyzed at the local laboratory of the phase I unit according to their standard routines.

Clinically significant laboratory values should be reported as AEs (see Section 6.7.7.1.1 for details).

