8.3.4.2 Laboratory Parameters

Abnormal laboratory values will be listed and their incidence, severity and relationship to the IMP will be tabulated for the IMP groups. Change from baseline will be summarized by IMP group. Individual changes (shift tables), individual clinically significant abnormalities and severity grading (mild, moderate, severe) will also be presented.

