## 15.3 Laboratory data

The list of laboratory parameters evaluated in this study is presented in Table 7. Laboratory values will be classified as within range/normal, abnormal high, or abnormal low, based on the local laboratory's normal ranges for the respective parameter.

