**Table 7 List of Laboratory Assessments**

Classification	Examination Component	Unit	Rounding Digit / Categories
Hematology	Hemoglobin	[g/dL]	0.1
	Hematocrit	[%]	0.1
	Platelet Count	[ $\times 10^{10}/L$ ]	0.1
	Red Blood Cells	[ $\times 10^{10}/L$ ]	1
	Leukocyte Total	[/ $10^6/L$ ]	1
	Neutrophils	[%]	0.1
	Lymphocytes	[%]	0.1
	Basophils	[%]	0.1
	Eosinophils	[%]	0.1
	Monocytes	[%]	0.1
	IgG	[mg/dL]	1
	IgA	[mg/dL]	1
	IgM	[mg/dL]	1
	Coagulation Profile (APTT)	[sec]	0.1
Biochemistry	Aspartate Aminotransferase (AST)	[IU/L]	1
	Alanine Aminotransferase (ALT)	[IU/L]	1
	Direct Bilirubin	[mg/dL]	0.1
	Total Bilirubin	[mg/dL]	0.1
	Uric Acid	[mg/dL]	0.1
	Alkaline Phosphatase	[U/L]	1
	Total Protein	[g/dL]	0.1
	Albumin	[g/dL]	0.1
	Prothrombin Time/International Normalized Ratio (PT-INR)	-	0.01
	Fibrinogen	[mg/dL]	1
	Complement C3	[mg/dL]	1

Urinalysis	Complement C4	[mg/dL]	1
	Cardiac Troponin	[ng/L]	0.1
	Creatinine	[mg/dL]	0.01
	C-reactive protein (CRP)	[mg/dL]	0.01
	Sodium	[mEq/L]	1
	Potassium	[mEq/L]	0.1
	Calcium	[mg/dL]	0.1
	Glucose	[mg/dL]	1
	Triglycerides	[mg/dL]	1
	HDL	[mg/dL]	1
	LDL	[mg/dL]	1
	BUN/Urea	[mg/dL]	0.1
	Erythrocytes	-	- , +- , + , 2+ , 3+ , 4+
	Leukocytes	-	- , +- , + , 2+ , 3+ , 4+
	Glucose	-	- , +- , + , 2+ , 3+ , 4+
	Ketones	-	- , +- , + , 2+ , 3+ , 4+
	pH	-	0.1
	Protein	-	- , +- , + , 2+ , 3+ , 4+
	Erythrocytes (Sediment) a)	-	
	Leukocytes (Sediment) a)	-	
	Protein (Sediment) a)		

a) Erythrocytes (Sediment), Leukocytes (Sediment), Protein (Sediment) will be shown only in listings.

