### 15.3.1 Descriptive Statistics of Laboratory Parameters

Population: Safety Analysis population

Group: Emapalumab, Placebo

Contents:

- Calculate the descriptive statistics of quantitative laboratory parameters (in Table 7 in Section 15.3 Laboratory data) at each analysis time point (defined in Table 3 in Section 8.4.3 Visit Windows) by groups.
- Conduct the same analysis by treatment groups and grades (Low/Normal/High).
- Conduct the same analysis for change from baseline.

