### **15.3.4      Contingency Table of Laboratory Parameters**

Population: Safety Analysis population

Group: Emapalumab, Placebo

Contents: 

- Create cross tables of normal range grading (Low/Normal/High) of quantitative laboratory parameters (in Table 7 in Section 15.3 Laboratory data) of baseline and at each analysis time point after IMP administration (defined in Table 3 in Section 8.4.3 Visit Windows) by groups.
- Remove data from calculation if both data from before and after IMP administration do not exist.

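### The SAP analyses the five differential cell types only as percentages of leukocytes, so no planned table or figure shows an absolute neutrophil or lymphocyte count (minor)

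*Protocol*

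**What the plan says.** Protocol Table 5 lists white blood cells and a "Differential blood count" among the haematology tests and does not say whether the differential is to be reported as percentages or counts. Protocol 8.3.4.2 promises shift tables and states "Change from baseline will be summarized by IMP group".

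SAP Table 7 fixes the units. It has "Neutrophils [%] 0.1" and "Lymphocytes [%] 0.1", with monocytes, eosinophils and basophils also in percent. The only white-cell row in absolute units is "Leukocyte Total" (its printed unit is read here as x10^6/L).

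SAP 15.3 then says "Laboratory values will be classified as within range/normal, abnormal high, or abnormal low", using the local laboratory's range for each parameter. SAP 15.3.1 gives descriptive statistics, the same by grade, and change from baseline. SAP 15.3.2 plots individual values, and SAP 15.3.4 says "Create cross tables of normal range grading (Low/Normal/High) of quantitative laboratory parameters". All three take the Table 7 parameters as listed. Neither document derives an absolute count for any of the five cell types.

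**The concern.** A differential percentage is a share of the total. If all white cells fall in proportion, every percentage is unchanged. If one cell type rises, the shares of the others fall even though their counts have not moved. A change from baseline or a Low/Normal/High shift computed on percentages therefore does not track the number of cells.

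Laboratory parameters are a named secondary endpoint, and the trial has six subjects on emapalumab and two on placebo, so single-subject shifts will be read closely. A fall in one cell type may go unattributed, and a percentage may be graded abnormal when the corresponding count has not changed.

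**Working it through.** The documents state no figure to reproduce and give no reference ranges. Cell counts and lower limits below are assumptions, varied where the result depends on them. The one formula is

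count = leukocyte total x percentage / 100.

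**1. A fall with no shift in either row.** Assume leukocytes go from 8000 to 3600 x10^6/L with neutrophils at 41% both times.
- Baseline count: 8000 x 0.41 = 3280. Later count: 3600 x 0.41 = 1476.
- Relative change: 1476/3280 - 1 = -55%.
- Neutrophil row: change from baseline 0.0 percentage points; Normal to Normal if the lower limit is 40%.
- Leukocyte row: change from baseline 3600 - 8000 = -4400; Normal to Normal if the lower limit is 3500, Low if it is 4000.

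When the mix of cells is constant, the percentage row never moves and only the leukocyte limit L can trigger a shift. The largest proportional fall from baseline W that gives no shift is 1 - L/W, taking a value at the limit as Normal:

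| Baseline leukocytes W | L = 3500 | L = 4000 |
|---|---|---|
| 5000 | 30% | 20% |
| 6000 | 42% | 33% |
| 8000 | 56% | 50% |

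A fall of half or more without a shift thus needs a baseline near 8000 in this grid; at lower baselines the unflagged fall is smaller.

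**2. A fall in neutrophils alone is understated.** Start from leukocytes 6000 at 60% neutrophils (3600), and let neutrophils halve to 1800. Leukocytes become 6000 - 1800 = 4200 and the percentage becomes 1800/4200 = 42.9%. The count has fallen by 50%, the percentage by 1 - 42.9/60.0 = 29% in relative terms.

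**3. An unchanged lymphocyte count with a falling percentage.** Assume lymphocytes 1800, neutrophils 3600 and other cells 600 (total 6000).
- Before: 1800/6000 = 30.0%.
- Neutrophils double to 7200: total 7200 + 1800 + 600 = 9600, and 1800/9600 = 18.75%, shown as 18.8%.
- This is Low at a lower limit of 20% or 25%, and Normal at 18%.

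The neutrophil multiple at which the unchanged lymphocyte count reaches a limit p is (1800/p - 1800 - 600)/3600: 2.11 for p = 18%, 1.83 for 20% and 1.33 for 25%. Over three assumed baselines with lymphocytes at 28% to 35%, the multiple ranges from 1.19 to 2.72.

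**4. Recovery from planned summaries.** Group mean counts cannot be obtained from the two sets of group means, because the mean of a product is not in general the product of the means. They can be obtained subject by subject from the listing.

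**The case against.** The strongest reply is that total leukocytes are analysed in absolute units in the same outputs. Because a count is the product of total and percentage, it cannot change while both analysed variables stay unchanged. In step 1 the leukocyte row shows a change of -4400. In step 3 the cause is also on view: leukocytes rise from 6000 to 9600 and neutrophils from 60.0% to 7200/9600 = 75.0%. A reader might infer that the plan can conceal a fall in neutrophils altogether. The documents do not support that. What stands is narrower: the fall is not attributed to a cell type, and the shift tables can show nothing.

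Second, all laboratory values are listed, quantitative ones are plotted per subject, and clinically significant values are reported as adverse events on the investigator's judgement (Protocol 6.7.7.1.1). With eight subjects, counts can be worked out by hand. This stands and lowers the severity, but none of it puts a count into a planned summary, shift table or figure.

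Third, a reader might infer a departure from the protocol, or a suspected fall in blood counts on emapalumab. Neither is supported. The protocol sets no unit for the differential. Protocol 4.4 links infection risk to neutralisation of IFN-gamma and to specific pathogens, and Protocol 4.1.2.3 reports no safety signal from clinical laboratory evaluations in the earlier healthy-volunteer study.

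**Conclusion.** The point holds as a minor gap in the laboratory analysis. No planned table, shift table or figure shows an absolute count for any of the five cell types. On assumed limits of 3500 x10^6/L and 40%, a 55% fall in neutrophils can pass without a shift in either row; at an assumed leukocyte limit of 4000, that same example would be flagged Low. A false Low for lymphocytes is possible but conditional: the worked value of 18.8% is Low at 20% or 25% and not at 18%. It would be wrong to conclude that such a false Low will occur, because the local laboratory's ranges are not in the documents. For the same reason, it cannot be said whether a neutrophil count of 1476 would itself be below that laboratory's range.

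**What to change.** In SAP Table 7 add five derived rows, one per cell type, as leukocyte total x percentage / 100 from the same sample. Include them in 15.3.1 (descriptive statistics and change from baseline), 15.3.2 and 15.3.4. Grade them against the local laboratory's count ranges where it has them; otherwise summarise them ungraded and say so. Keep the percentage rows as supportive, since those are the values that the SAP already plans to grade.

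The cost is five derived variables and one request to the laboratory for its count ranges. Both inputs come from the haematology assessment already scheduled at the same visits, so no extra sample or visit is needed. The protocol text need not change, because it sets no unit. SAP 5.2 allows a revision before database lock.

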6.7.7.3 Vital signs

Vital signs (body temperature, heart rate, and semi-supine systolic and diastolic blood pressure will be measured at all study visit at timepoint indicated the schedule of events (Table 3) and recorded in the CRF.

Clinically significant abnormal vital signs values should be reported as AEs (see Section 6.7.7.1.1 for details).

6.7.7.4 Physical examination

A complete physical examination will be performed at screening and at the Study Completion Visit. At all other visits brief physical examinations will be performed, only if indicated.

The complete physical examination will be performed by a physician and will include examination of the following: general appearance, eyes, ears, nose, throat, chest/respiratory, heart/cardiovascular, gastrointestinal/liver, musculoskeletal/extremities, dermatological/skin, thyroid/neck, lymph nodes, and neurological/psychiatric. Each component will be recorded as “normal” or “abnormal” at each visit. Abnormalities should be described.

If any abnormalities are reported at baseline they should be recorded as medical history. New or worsening of abnormalities should be reported as AEs (see Section 6.7.7.1.1 for details).

6.7.7.5 Electrocardiograms

A 12-lead ECG recording will be performed at screening, at Study Day 1 pre-infusion and at 4h post-infusion, and at the study completion visit. The ECG assessments will be performed at the phase I unit and will be reported as “normal” or “abnormal” in the CRF. Any abnormalities should be specified. Abnormalities reported at screening should be recorded as medical history.

Clinically significant abnormal ECG findings should be reported as AEs (see Section 6.7.7.1.1 for details).

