To investigate immunogenicity of emapalumab

STUDY ENDPOINTS

Primary endpoint: PK parameters: Cmax, tmax, CEOI, AUClast, AUCinf, %AUCextr, λ_z , $t_{1/2}$, CL, Vss, MRTlast and MRTinf

PD biomarkers:
Pre-dose circulating IFN γ concentration
Total IFN γ concentrations
CXCL9 concentration
sIL2R concentration

Secondary endpoint(s): Adverse Events
Laboratory parameters
The presence of anti-drug antibodies (ADAs) and neutralizing antibodies (nAbs)

STUDY DESIGN AND METHODS

Study design: This is a randomized, placebo controlled and double-blinded study to evaluate the PK, PD and safety of a single dose (1 mg/kg) of emapalumab in adult healthy Japanese subjects.

Number of subjects planned: 8

Diagnosis and main criteria for inclusion:	Healthy volunteers, age between 20 to 50 (inclusive)
Assessments for pharmacokinetic (PK) and pharmacodynamics (PD) evaluation:	Serum concentration vs time profiles are obtained for determination of emapalumab PK/PD variables at Study Days 1, 2, 3, 5, 8 and Weeks 2, 4, 6, 10 and 14.
Assessment for safety evaluation:	Adverse events are collected from the time of investigational product administration until last study visit (Week 14) Heart rate, blood pressure, body temperature are assessed at Screening, Study Day -1 prior to the infusion, every 30 minutes after infusion up to 2 hours post infusion, every hour from 4 hours post infusion up to 8 hours post infusion, 10 and 12 hours post infusion, Study Days 2, 3, 5, 8, Weeks 2, 4, 6 and 14. Blood and urine samples for local laboratory analyses of hematology, clinical chemistry and coagulation are collected at Screening, Study Days -1, 1, 2, 3, 5, 8, Weeks 2, 4, 6, 10 and 14 12-lead ECGs are obtained at Screening, prior to the infusion on Study Day 1, after the infusion, and at last study visit (Week 14) A physical examination will be performed at Screening, Study Day -1 and at last study visit (Week 14) Blood samples for central laboratory analyses of ADAs are collected at Study Day -1 pre-infusion and at Week 14.
Test product; dose and mode of administration:	Emapalumab 5 mg/mL for i.v. infusion
Reference product; dose and mode of administration:	Saline 0.9% for i.v. infusion
Duration of treatment(s):	Single dose
Determination of sample size:	No formal sample size calculation. 6 subjects receiving emapalumab are considered sufficient, considering the inter-subject variability in the PK results from earlier studies.

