6.7.5 Pharmacokinetics

PK blood samples, to measure serum levels of emapalumab, will be collected for all subjects receiving study treatment.

At Study Day 1 sampling should be done pre-dose and at end of infusion, 2, 4, 8, and 10h post dose. PK samples will thereafter be collected on all study visits. It should be noted that a separate i.v. line will have to be used when collecting the PK samples, i.e. not the same i.v. line as used for the i.v. infusion of study treatment.

The date and time of blood sampling will be recorded in the CRF.

Samples will be sent to central laboratory for analysis. The procedures for blood collection, processing into serum, storing and transporting to the central laboratory as well as the laboratories responsible for the analysis are fully described in the laboratory manual.

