### 8.4.3 Visit Windows

The visit windows for PK and PD assessments are displayed in Table 1, for Vital signs in Table 2 and for other assessments in Table 3. The analysis time points, based on the visit windows, will be used for analysis. In addition, let the IMP administration date be Day 1.

For descriptive statistics, in the case a parameter is not available on the specified analysis timepoint, the visit window is to be applied. Priority will be given to scheduled visits; unscheduled visits will be used if no scheduled visits occurred within the analysis visit window.

If there is more than one observation during the visit window, a value will be selected as follows: the value closest to the actual analysis timepoint in question (eCRF) will be chosen first. In the case that there are 2 values equidistant to the analysis timepoint of interest, the observation that is before the analysis timepoint in question (eCRF) will be selected. In the case of 2 or more measurements on the same date, the earliest measurement will be selected.

**Table 1** Visit Window of pharmacokinetic and pharmacodynamic assessment

Analysis time point		Visit Window	Pharmacokinetics	Pharmacodynamics
Day 1	Preinfusion	Before IMP administration	X	X
	1 hr	55 min to < 65 min	X a)	X
	2 hr	1 hr 55 min to < 2 hrs 5 min	X	X
	4 hr	3.75 hr to <4.25 hr	X	X
	8 hr	7.5 hr to <8.5 hr	X	X
	10 hr	9.5 hr to <10.5 hr	X	X
Day 2		Day 2	X	X
Day 3		Within Day 3	X	X
Day 5		Within Day 5	X	X
Day 8		Within Day 8	X	X
Follow-up Week 2		Day 12 to Day 16	X	X
Follow-up Week 4		Day 26 to Day 30	X	X
Follow-up Week 6		Day 40 to Day 44	X	X
Follow-up Week 8		Day 54 to Day 58	X	
Follow-up Week 10		Day 68 to Day 72	X	
Follow-up Week 12		Day 82 to Day 86	X	
Study Completion Visit (Week 14)		Day 96 to Day 100	X	X
Withdrawal (WD)		When the subject is withdrawn	X	X

a) At end of infusion.

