**Table 3** **Visit window of the other items**

Analysis time point	Visit Window	Laboratory a)	ADA	Physical Examination c)	12-lead ECG	Pregnancy Test d)
Screening	Within 21 days prior to IMP administration	X		X	X	
Day -1	Within Day -1	X		X		
Day 1	Preinfusion	Before IMP administration within Day 1		X	X	

Analysis time point		Visit Window	Laboratory a)	ADA	Physical Examination c)	12-lead ECG	Pregnancy Test d)
1 hr 2 hr 4 hr 8 hr 10 hr 12 hr	1 hr	0.75 hr to <1.25 hr					
	2 hr	1.75 hr to <2.25 hr					
	4 hr	3.5 hr to <4.5 hr	X			X	
	8 hr	7.5 hr to <8.5 hr					
	10 hr	9 hr to <11 hr					
	12 hr	11 hr to 13 hr					
Day 2	Within Day 2	X					
Day 3	Within Day 3	X					
Day 5	Within Day 5	X					
Day 8	Within Day 8	X					
Follow-up Week 2	Day 12 to Day 16	X					
Follow-up Week 4	Day 26 to Day 30	X					X
Follow-up Week 6	Day 40 to Day 44	X					
Follow-up Week 8	Day 54 to Day 58						X
Follow-up Week 10	Day 68 to Day 72	X b)					
Follow-up Week 12	Day 82 to Day 86						X
Study Completion Visit (Week 14) / Withdrawal (WD)	Day 96 to Day 100 or when the subject is withdrawn	X	X	X	X	X	

a) Laboratory includes hematology, chemistry, and urine and hematology measurements, taken under fasting condition except from screening.

b) Only hematology and chemistry.

c) A full physical examination will be performed at screening and at Week 4 visit. At all other visits brief physical examinations will be performed, only if indicated.

d) Urine pregnancy test is to be performed with a dipstick at week 4, 8, 12 and study completion.

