V ss	
Steady state volume of distribution
 
Calculate from the following formula in subjects whose <math>\lambda_z</math> can be calculated.
 $V_{ss} = CL \times MRT_{inf}$ 
Vss is calculated using dose level (mg/kg) and actual dose (mg).
	L	3 significant figures
MRT last	
Average residence time from the start of infusion to the final blood collection time
 $= \frac{AUMC_{last}}{AUC_{last}} - \frac{TI}{2}$ 
TI :Duration of infusion
	h	3 significant figures
MRT inf	
Average residence time from start of infusion to infinite time
 $= \frac{AUMC_{inf\_calc}}{AUC_{INF\_calc}} - \frac{TI}{2}$ 
TI :Duration of infusion
	h	3 significant figures

Subjects will be excluded from the PK analysis if their data do not allow for accurate assessment of the PK (e.g. incomplete administration of the study drug; subject vomited after receiving study drug; missing information of dosing and sampling times; concentration data not sufficient for PK parameter calculation).Following rules will be applied for descriptive statistics.

- Lower Limit of Quantification (LLOQ) will be substituted with 0.
- The number of subject displayed as "N" on summary tables will be the number of subject whose serum concentrations are measured (include LLOQ) or PK parameters are calculated.
- When the time of blood collection is outside the time windows, the relevant serum concentration will be listed but excluded from the calculation of summary statistics.

**Table 5** List of compound and lower limit of quantification

Compound	Unit	Lower Limit of Quantification	Rounding Digit
Emapalumab	ug/L	62.5 ug/L	0.01

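### Day 1 has no single stated time origin, and the fixed end-of-infusion PK window does not follow an infusion that may last up to 2 hours

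*Protocol*

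**What the plan says.** Day 1 times are expressed in several ways.

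- **Protocol Table 4** heads its Day 1 columns in hours post start. Footnote 9 marks the 1 h PK sample as the end of infusion.
- **Protocol 6.7.7.5** places the ECG "at Study Day 1 pre-infusion and at 4h post-infusion".
- **Protocol synopsis** takes vital signs "every 30 minutes after infusion up to 2 hours post infusion, every hour from 4 hours post infusion up to 8 hours post infusion", then at "10 and 12 hours post infusion". The body section on vital signs (6.7.7.3) gives no times and defers to the schedule of events. It cites that as Table 3, but the schedule is Table 4.
- **Protocol 6.7.5** asks for PK samples pre-dose, at end of infusion, and at "2, 4, 8, and 10h post dose".
- **SAP 8.4.3, Table 1** gives the 1 hr PK/PD point a window of 55 to <65 min, footnoted for PK as end of infusion. The 2 hr window is "1 hr 55 min to < 2 hrs 5 min".
- **SAP Tables 2 and 3** list hour windows for vital signs, ECG and laboratory tests with no origin. The only post-dose Day 1 ECG window is "3.5 hr to <4.5 hr".

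The infusion is planned for 1 h but may be extended to 2 h (Protocol 6.3.1 and 6.6.4). When a PK sample is outside its window, SAP 14.1 says that "the relevant serum concentration will be listed but excluded from the calculation of summary statistics".

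**The concern.** If the text is counted from the end of infusion and the SAP windows from the start, the two clocks differ by the length of the infusion. That is 1 h as planned and up to 2 h, whereas the ECG window extends only half an hour either side of 4 h. An assessment done exactly as the text asks could then be placed in another row of the SAP tables, or in none.

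The end-of-infusion sample raises a second problem that does not depend on how the wording is read. Its window is fixed in minutes from the start, but the event it marks moves with the infusion. With six emapalumab subjects, each excluded concentration removes one-sixth of the data at that point of the summary table and mean curve.

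**Working it through.** **Rule.** Time from start = stated time + offset. The offset is 0 if times run from the start of infusion, and the infusion length T if they run from its end. Each result is compared with the half-open SAP windows.

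**Step 1: fix the SAP Table 1 clock.** An infusion with T = 60 min ends 60 min from the start, inside 55 to <65 min. The 1 hr = end-of-infusion label is reproduced only if the clock begins at the start, as in Protocol Table 4. Tables 2 and 3 share the hour labels, so a start clock there is an inference.

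**Step 2: offset 0.**
- ECG: 4.0 h, inside its window.
- PK: 2, 4, 8 and 10 h, all four inside their windows.
- Vital signs: the synopsis gives 11 times (0.5, 1, 1.5, 2, 4, 5, 6, 7, 8, 10 and 12 h). Ten fall in the row of the same name. The 0.5 h reading has no row, and SAP rows 2.5, 3, 3.5 and 9 hr have no synopsis reading.

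**Step 3: offset 1 h, the literal end-of-infusion reading.**

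| Assessment | Stated time | From start | SAP result |
|---|---|---|---|
| ECG | 4 h | 4 + 1 = 5 h | outside 3.5 to <4.5 h, by 0.5 h |
| Vital signs | 0.5, 1, 1.5, 2 h | 1.5, 2, 2.5, 3 h | on the rows of those names |
| Vital signs | 4, 5, 6, 7, 8 h | 5, 6, 7, 8, 9 h | on the rows of those names |
| Vital signs | 10 h | 11 h | in the 12 hr row (11 to <13 h); 10 hr row empty |
| Vital signs | 12 h | 13 h | in no row (<13 h) |

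So 10 of the 11 vital-signs readings still fall in a window. With a 2 h infusion the ECG is at 4 + 2 = 6 h.

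**Step 4: which reading does the wording favour?** For vital signs, counting from the start puts the first half-hourly reading at 0.5 h, in the middle of a 1-hour infusion, so it could not be after infusion. Counting from the end puts the four half-hourly readings exactly on existing SAP rows. For PK, end of infusion is listed as a sample in its own right and is not given as the origin. Counting from the start fits Table 4 and every Table 1 window.

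**Step 5: the end-of-infusion PK sample.** Taken correctly, it is drawn at time T from the start. The 2 hr window opens at 115 min.

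| T | SAP Table 1 window |
|---|---|
| 55 to <65 min | 1 hr, as intended |
| 65 to <115 min (e.g. 90) | none; excluded under SAP 14.1 |
| 115 to 120 min | 2 hr; 1 hr row empty for that subject |

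**The case against.** **No text defines the terms as counted from the end.** Protocol 6.7.1.3 uses a Post-infusion heading for procedures after the start of administration and sends the site to Table 4. This stands as a reason not to treat the end-of-infusion reading as fact. It does not settle the matter, because that heading also covers randomization and the infusion itself, and the half-hourly vital signs point the other way.

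**A reader might infer that the 2, 4, 8 and 10 h PK samples are lost.** If post dose meant after the infusion, they would fall at 3, 5, 9 and 11 h and miss all four windows. The documents do not support this: the start-based reading is consistent throughout. PK parameters are also calculated from actual times (SAP 14.1), so they are unaffected either way.

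**A reader might infer that vital signs are generally misplaced.** They are not. A reading taken 5 h from the start and shown in the 5 hr row is in the right row on the SAP's clock. One reading is assigned to the wrong row and one misses.

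**ECG loss is not certain.** SAP 8.4.3 applies windows when no value is available at the specified time point, so an ECG entered in the eCRF as the 4 h reading may still be tabulated. The same section bases analysis time points on the windows, which leaves the question open. The explicit exclusion rule covers serum concentrations only. ECG is not an endpoint, ECGs are listed, and clinically significant findings are reported as adverse events. This limits the consequence but not the inconsistency.

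**Table 1 already footnotes the 1 hr PK sample as end of infusion.** It does, but the fixed window stays beside it and SAP 14.1 excludes samples outside their windows.

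**Conclusion.** The point holds in two parts.

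1. **Time origin.** The documents state no single Day 1 origin, and their wording conflicts. On the literal reading with a 1-hour infusion, the sole post-dose Day 1 ECG is 0.5 h beyond its window's upper limit, one vital-signs reading is placed in the wrong row and one in none. This assumes that SAP Tables 2 and 3 run from the start and that an eCRF label does not override the window. The position of the post-dose ECG mark in Table 4 was not used, because its column cannot be read reliably in the available text.
2. **End-of-infusion PK window.** This holds on either reading of the wording. Once an infusion reaches 65 min, a correctly taken end-of-infusion sample is dropped from the concentration summaries or falls in the 2 hr window. How often this would happen is unknown, since the documents give no expected frequency of prolonged infusions.

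The effect is on descriptive tables and mean curves. PK parameters are not affected, and no hypothesis test is planned.

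**What to change.** - **One origin.** The sponsor chooses the Day 1 time origin and reconciles the synopsis, 6.7.5 and 6.7.7.5 with Protocol Table 4. Which assessment times are clinically right is not for this review.
- **State it in the SAP.** Add the origin to Tables 1 to 3 and align the ECG and vital-signs windows to it. Do not shift all SAP windows by the infusion length: Table 1 already equates 1 hr with the end of infusion and would break.
- **End-of-infusion PK sample.** In SAP Table 1, define this window relative to the recorded end of infusion instead of 55 to <65 min from start. Protocol 6.6.4 already has the infusion end time recorded in the CRF.

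The cost is minor wording and programming. The end-of-infusion row may then combine somewhat different elapsed times, which a footnote can state.
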